## 5.2 Pre-treatment Evaluation

Clinical: required on Cycle 1 Day (-28) or within 28 days before the treatment initiation

- 5.2.1 History and physical examination, including height, weight, and vital signs
- 5.2.2 Performance status evaluation
- 5.2.3 Laboratory /Diagnostic: required within 28 days before the treatment initiation.
  - 5.2.3.1 CBC, platelet count and differential
  - 5.2.3.2 Serum chemistries: includes BUN, Creatinine, ALT, and AST, glucose, alkaline phosphatase, total bilirubin, TSH and LDH. If TSH is abnormal a T3 and T4 level will be required.
  - 5.2.3.3 Testosterone, DHEA, DHEA-S, and AD, Direct Renin and Aldosterone/Direct Renin Ratio serum level
  - 5.2.3.4 PSA
  - 5.2.3.5 Study blood draw for the measurement of serum steroids concentration
  - 5.2.3.6 Imaging/Diagnostic: will be performed at the discretion of the treating physician. Obtaining prostate MRI is preferred but not mandatory for the study enrollment.

## 5.3 Registration process

To register a patient, the following documents should be completed by the research nurse and e-mailed to the Study Coordinator:

- Registration Form
  - Eligibility Worksheet
  - Copy of source documentation (required laboratory tests, radiographic scans (if applicable), physician notes, nursing notes, list of medications, pathology/surgical reports, etc.)
- Signed patient consent form to complete the registration process, the Coordinator will
- Verify patient eligibility worksheet is complete
  - Request additional documentation if necessary
  - Assign a patient study number
  - Register the patient on the study using the ONCORE database

- 6 E-mail a letter of Confirmation of Registration, including the patient study number, to the responsible research nurse treatment plan.

## 6.1 Packaging, Storage, and Labeling

Apalutamide will be supplied as 60mg tablets packaged in 30-ct, 120 cc HDPE bottles with child-resistant closures and tamper proof heat induction seals. At the clinical and at the patient's home, the study drug should be stored at room temperature and protected from heat; do not freeze. Each bottle of study drug will be labeled with the required regulatory agency warning statement, the protocol number, and directions for patient use and storage. The Investigator will ensure that the study drug is stored in appropriate conditions in a secure location with controlled access.

## 6.2 Dosage and Administration

### 6.2.1 Description of Study agents and Administration

Study agents include Apalutamide and leuprolide. Apalutamide will be provided by the study. Subjects are to receive the following:

- Leuprolide 7.5 mg IM x 1 dose on day (-28)  $\pm$  3 days
- Apalutamide 240 mg (4 x 60 mg tablets) by mouth [PO] on a continuous once-daily dosing regimen.

Sufficient study medication for an entire treatment course till the day of surgery will be distributed on the first day of treatment. Apalutamide will be self-administered on an outpatient basis during the study, once daily, with or without food. Treatment will start on Day (-28)  $\pm$  3 days from the scheduled date for radical prostatectomy. Subjects may take Apalutamide up to and including the day before radical prostatectomy, at which time the medication will be discontinued.

It is anticipated that individual patients may occasionally forget to take a dose. In those cases, missed doses should only be replaced if the patient remembers within a 12-hour window. After that, patients should just take the next dose the following day, without compensating for the missed dose.

## 6.3 General Concomitant Medication and Supportive Guidelines

### 6.3.1 Pre-study therapy

To be eligible for this study, subjects must have a new diagnosis of prostate cancer with no history of previous treatments for prostate cancer.

### 6.3.2 Concomitant therapy

All patients should be maintained on the same medications throughout the entire study period, as medically feasible, with minimum introduction of new chronic therapies. Standard medical treatment as applicable is allowed except for treatments noted in the exclusion criteria and/or listed in the prohibited medications section below.

#### 6.3.2.1 Prohibited medications and treatments

As a class effect, androgen receptor antagonists have been associated with seizures due to an off-target mechanism of action (GABAA inhibition).

To date, no patients receiving Apalutamide have experienced seizures, however, in preclinical experiments, at very high doses, dogs treated with Apalutamide had tremors and generalized seizures. Patients will be closely monitored for seizures, but as a precautionary measure, drugs known to decrease the seizure threshold and/or cause seizure will be prohibited while on study. A list of the medications which are PROHIBITED while on study:

- Aminophylline/theophylline
- Atypical antipsychotics (e.g., clozapine, olanzapine, risperidone, ziprasidone)
- Bupropion
- Lithium
- Meperidine and pethidine
- Phenothiazine antipsychotics (e.g., chlorpromazine, mesoridazine, thioridazine)
- Tricyclic and tetracyclic antidepressants (e.g., amitriptyline, desipramine, doxepin, imipramine, maprotiline, mirtazapine)
- Herbal products that may have hormonal anti-prostate cancer activity and/or are known to decrease PSA levels (e.g. saw palmetto). All herbal supplements must be discussed with the study provider and discontinued at the provider's discretion.
- Current systemic steroid or corticosteroid therapy (inhaled or topical steroids are also not allowed), unless waived at the provider's discretion.

**[Please see the appendix IV for a more comprehensive list (with brand names)]**

#### 6.3.2.2 Restricted Concomitant Medications

- Apalutamide is metabolized primarily by human CYP3A4, thus co-administration with strong inhibitors or inducers of CYP3A4 should be avoided as much as possible. Apalutamide may also induce CYP3A4; therefore, caution should be taken when administered in conjunction with CYP3A4 substrates that have a narrow therapeutic index. Examples of the strong CYP3A4 inhibitors and inducers include the following:

- **Strong CYP3A4 inhibitors:** itraconazole, clarithromycin, erythromycin, diltiazem, verapamil, delavirdine, atazanavir, indinavir, nefazodone, nelfinavir, ritonavir, saquinavir, telithromycin, voriconazole, grapefruit juice (or grapefruits); co-administration with any of these agents may increase Apalutamide plasma concentrations
- **Strong CYP inducers:** phenytoin, carbamazepine, rifampin, rifabutin, rifapentin, phenobarbital, efavirenz, tipranavir, St. John's wort; co-administration with any of these agents may decrease Apalutamide plasma concentrations
- Apalutamide may also induce CYP3A4; therefore, caution should be taken when administered in conjunction with CYP3A4 substrates that have a narrow therapeutic index
- The potential for drug-drug interaction between Apalutamide and warfarin (e.g., Coumadin) is unknown at present. If a patient is taking Coumadin, re-assess PT/INR as clinically indicated and adjust the dose of Coumadin accordingly.
- Corticosteroids: due to possible resistance mechanisms which may be contributed by glucocorticoid receptor signaling, concurrent use of corticosteroids during the study is not recommended.
- Avoid grapefruit and pomegranate juice and/or fruits

### 6.3.3 Life style guidelines

Patients of childbearing potential must agree to practice some form of effective contraception, such as vasectomy, double barrier contraception, or sexual abstinence prior to entering into the study and for 6 months following the last dose of study drug.

There are no dietary restrictions with the exception of grapefruit and pomegranate fruits and/or juice while the patient is on study. Study treatment can be taken with or without food.

## 6.4 Duration of Therapy

All patients will be treated with one dose of leuprolide given IM on day  $(-28) \pm 3$  days followed by Apalutamide starting on day  $(-28) \pm 3$  days from the date of RP. The treatment will start on Day  $(-28) \pm 3$  days which is set based on the scheduled date of RP and will be continued till the day of surgery.

## 6.5 Measures of Treatment Compliance

All patients will complete a daily diary documenting the intake of Apalutamide

At post-op follow up visit, patients will be asked to return any remaining study drug as well as all used and unused study drug containers.

Treatment compliance will be defined as the number of tablets taken divided by the expected number of tablets and reported as percentage. In case of dose reductions, the expected number of tablets should reflect the new dose level.

Tablets that are not returned will be considered to have been taken, unless otherwise specified in the case report form (CRF).

## 6.6 Duration of Follow up

All patients will be evaluated within 4-8 weeks after RP to rule out any potential AEs after discontinuation of the treatment. Any clinically significant abnormalities persisting at the end of the study will be followed by the investigator until resolution or until a clinically stable endpoint is reached. If patient has no AEs with regards to study agents this will be the last study related follow up.

## 7 Dose Delays/ Dose Modifications

### 7.1 Safety Monitoring

Thyroid stimulating hormone (TSH) should be evaluated throughout the study (with T3 and T4 done only if TSH is abnormal) as follows:

- Cycle 1, Day (-28) or within 28 days before treatment initiation
- Pre-Op Evaluation
- Follow Up Visit

### 7.2 Apalutamide Dose Modifications in the Event of Toxicity

Dose interruptions and/or reductions for each patient will be permitted provided that study discontinuation criteria have not been met (please see Section 9.16 End of Treatment).

- Patients experiencing Grade 3 treatment-related adverse events will have study drug held until the severity of the toxicity decreases to Grade 1 or returns to baseline. If improvement occurs within 7 days, dosing may be restarted at the next level dose reduction. Exception to hold includes clinically insignificant lab abnormalities and hypertension, as deemed by the treating physician. Events that can be mitigated with optimal treatment within 2 days of the occurrence do not require a dose reduction; dose may resume at previous level.
- Any patient experiencing a drug related Grade 4 toxicity of any duration will be permanently discontinued.
- Patients experiencing treatment-related seizure of any grade or grade (G) 4 neurotoxicity will have study drug permanently discontinued.
- At any given dose level, if patients experience gastrointestinal (GI) discomfort due to the number of tablets, they will be allowed to switch to a BID regimen as needed.
- A maximum of one dose level reduction will be allowed.  
Any patient requiring Apalutamide treatment interruption longer than 7 days during the treatment period will meet the criteria for end of study treatment and study discontinuation.

**Table 1.** Apalutamide Dose Levels

Toxicity	Dose of Apalutamide (assuming 240 mg/day dosing)
Grade 1 or 2	No change
≥Grade 3 or higher	Hold until Grade 1 or baseline, resume at full dose
First Recurrence ≥Grade 3	Hold until Grade 1 or baseline, resume at 180 mg (3 tablets)
First occurrence of seizure of any grade or Grade 4 neurotoxicity	Discontinue
More than 7 days off treatment due to treatment related toxicity	Discontinue

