### Clinical Studies with Apalutamide

Study ARN-509-001 is an ongoing Phase 1/2 study in subjects with progressive CRPC. In the Phase 1 component of the study, 30 subjects with metastatic CRPC (mCRPC) received at least 1 dose of Apalutamide at escalating dose levels ranging from 30 to 480 mg/day. All subjects received Apalutamide orally once daily, except those in the 300-, 390-, and 480-mg cohorts who received a twice-daily dosing regimen. There was 1 dose-limiting toxicity (DLT) observed at the 300-mg dose level (Grade 3 treatment-related abdominal pain). The event lasted 6 days and resolved with dose interruption and subsequent dose reduction to 240 mg (120 mg twice daily). Three additional subjects were treated at the 300-mg dose level with no reported DLTs. No seizures were reported at any dose level. The maximum tolerated dose (MTD) was not determined. The pharmacokinetics (PK) profile was determined to be linear and dose-proportional. The dose of 240 mg was chosen as the dose for subsequent phase III studies.

Ninety-seven subjects are being evaluated in the Phase 2 portion (Cohort 1: non-metastatic [NM]-CRPC n=51; Cohort 2: mCRPC without previous ketoconazole, abiraterone acetate/prednisone, enzalutamide or chemotherapy [for mCRPC] n=25; and Cohort 3: mCRPC post abiraterone acetate/prednisone and no previous chemotherapy [for mCRPC] n=21). Treatment-related adverse events (AEs) in the Phase 2 portion that have been reported to date in >10% of the subjects across the 3 cohorts included fatigue, diarrhea, nausea, abdominal pain, hot flush, hypothyroidism, decreased blood thyroid stimulating hormone, dysgeusia, decreased appetite (including weight loss), and skin rashes. In the Phase 2 portion, no serious adverse events (SAEs) were assessed as treatment-related. The safety profile of Apalutamide is consistent with the preclinical pharmacology and toxicology, and is as expected for an AR antagonist.

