### 9.16 End of Treatment

A patient may be discontinued from study treatment at any time if the patient, the Investigator and his (her) team, feels that it is not in the patient's best interest to continue on study. The following is a list of possible reasons for early discontinuation of study treatment:

- Disease progression
- Any episode of seizure
- Any other adverse event that cannot be adequately managed with dose modifications, including dose interruption for up to 7 days
- Protocol violation requiring discontinuation of study treatment
- Patient is not compliant with study procedures
- Lost to follow-up
- Patient withdrawal of consent
- Sponsor request for early termination of study

Patients will be followed for at least 28 +/-7 calendar days after the last dose of study drug. If a patient is withdrawn from treatment due to an adverse event, the patient will be followed until the adverse event has resolved or stabilized as per Section 7.6.

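### Section 7.2 permanently stops apalutamide after a drug-related Grade 4 toxicity, while its own Table 1 resumes it at full dose; the two also differ for a first Grade 3 event

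*Combined protocol and SAP*

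**What the plan says.** Section 7.2 sets the apalutamide dose rules twice, as bullets and then as Table 1.

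- **Grade 4, bullet:** "Any patient experiencing a drug related Grade 4 toxicity of any duration will be permanently discontinued". A separate bullet stops the drug for treatment-related seizure of any grade or Grade 4 neurotoxicity.
- **Grade 3, bullet:** a treatment-related event is held until Grade 1 or baseline, and "If improvement occurs within 7 days, dosing may be restarted at the next level dose reduction". There are two carve-outs. Clinically insignificant laboratory abnormalities and hypertension need no hold, as the treating physician judges. Events brought under control within 2 days may resume at the previous dose.
- **Limit on reductions:** "A maximum of one dose level reduction will be allowed". An interruption longer than 7 days ends study treatment.
- **Table 1, row for Grade 3 or higher:** "Hold until Grade 1 or baseline, resume at full dose".
- **Table 1, row for first recurrence at Grade 3 or above:** "Hold until Grade 1 or baseline, resume at 180 mg (3 tablets".
- **Table 1, discontinuation rows:** seizure of any grade or Grade 4 neurotoxicity, and more than 7 days off treatment for treatment-related toxicity.

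Section 7.2 refers to Section 9.16 for the discontinuation criteria. That list names seizure and, more generally, "Any other adverse event that cannot be adequately managed with dose modifications, including dose interruption for up to 7 days". It has no item for Grade 4 toxicity.

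**The concern.** A life-threatening drug reaction is where a dose table most needs to be unambiguous. Staff working from the table would re-challenge at full dose a man whom the text has permanently taken off drug.

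The trial's conduct offers few built-in checks. Section 6.2.1 dispenses the whole course on the first day for self-administration at home. The Section 11 calendar shows no scheduled visit between Day (-28) and the pre-operative evaluation 1 to 3 days before surgery. Section 1.2 describes the drug as still investigational in this pre-surgical use.

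The Grade 3 mismatch is secondary. It changes the restart dose for a subset of men but does not reverse a stopping rule.

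**Working it through.** The plan states no figure to reproduce here. The check is a comparison of the two sets of rules, followed by dose arithmetic.

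**Inputs.** Full dose is 4 × 60 = 240 mg and the only reduced level is 3 × 60 = 180 mg (Section 6.2.1, Table 1). The planned course is 28 days (Section 3.1). The sample size is 57 and the accrual goal is up to 80 (Section 14.1).

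**Rules side by side: daily dose after the event**

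| Event | Bullets | Table 1 |
|---|---|---|
| Drug-related Grade 4, not seizure or neurotoxicity, recovered within 7 days, doses left | 0 mg | 240 mg |
| The same, if it falls in the recurrence row | 0 mg | 180 mg |
| First treatment-related Grade 3, recovered within 7 days, not controlled within 2 days, outside the laboratory/hypertension exception, doses left | 180 mg | 240 mg |
| Seizure or Grade 4 neurotoxicity | stop | stop |
| More than 7 days off drug | stop | stop |

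The first three rows conflict and the last two agree. Events too close to surgery for any restart also end the same way under both rules. The 180 mg in the third row is inferred: the bullet says the next lower level, and Table 1 has only one. Table 1 gives Grade 4 neurotoxicity its own stop row, which implies that other Grade 4 events belong in the hold-and-resume row. The Summary of Changes lists an edit to Section 7.1 but none to Section 7.2, so both rules are current text.

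**Daily difference.** Grade 4: 240 − 0 = 240 mg. First Grade 3: (240 − 180)/240 = 25%.

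**Cumulative difference.** The planned course is 28 × 240 = 6,720 mg. Doses left = 28 − dose number at the event − days held. Event timing and hold length are assumptions.

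| Event after dose | Days held | Doses left | Grade 4 gap (× 240 mg) | Grade 3 gap (× 60 mg) |
|---|---|---|---|---|
| 7 | 6 | 15 | 3,600 mg (54%) | 900 mg (13%) |
| 14 | 6 | 8 | 1,920 mg (29%) | 480 mg (7%) |
| 21 | 7 | 0 | 0 | 0 |

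**Frequency.** The documents give no expected Grade 3 or 4 rate. Section 1.2 reports 1 dose-limiting toxicity among 30 Phase 1 subjects. Of the 97-subject Phase 2 portion it says: "In the Phase 2 portion, no serious adverse events (SAEs) were assessed as treatment-related". With an assumed drug-related Grade 4 rate p, the expected number is n × p and the chance of at least one in 80 men is 1 − (1 − p)^80.

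| Assumed p | Expected in 57 | Expected in 80 | At least one in 80 |
|---|---|---|---|
| 0.5% | 0.29 | 0.40 | 33% |
| 1% | 0.57 | 0.80 | 55% |
| 3% | 1.71 | 2.40 | 91% |

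The last column is the chance of any drug-related Grade 4 event, not the chance that the conflict applies. If one in four such events met the recovery and timing conditions (a further assumption), the effective rates would be 0.125% and 0.75%. The chance of at least one affected man in 80 would then be 1 − 0.99875^80 ≈ 10% to 1 − 0.9925^80 ≈ 45%.

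**Is the Grade 3 window realistic?** The one Phase 1 dose-limiting toxicity was Grade 3: "The event lasted 6 days and resolved with dose interruption and subsequent dose reduction to 240 mg (120 mg twice daily". Six days is longer than 2 and within 7, and the management matched the bullets. It arose at the 300-mg level in metastatic castration-resistant disease.

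**The case against.** The strongest reply is that the bullet already governs. It is mandatory, specific and unconditional, and Section 7.2 permits holds and reductions only while discontinuation criteria have not been met. On that reading the hold-and-resume rows apply only to men not already stopped, and the silence of Section 9.16 proves little because its list gives possible reasons and is not exhaustive. This is the sensible clinical reading, but no sentence says so, and the separate neurotoxicity row points the other way.

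A second reading confines the Grade 3-or-higher row to events not related to the drug. The row carries no such limit, so it still covers drug-related events.

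Other points do stand:

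- Both rules interrupt the drug at once, and the table resumes only at Grade 1 or baseline.
- The investigator may stop treatment at any time (Section 9.16), and serious events go to the company within 24 hours (Section 9.7.1) and to the toxicity committee (Section 9.13). These safeguards lower the risk of an unconsidered re-challenge without removing the ambiguity.
- Harm requires a rare event, quick recovery, doses left and staff following the table against the bullet.
- The Phase 1 case was reduced to 240 mg, which is this trial's full dose. It therefore does not show that 240 mg needs lowering; it only shows that an event of that duration occurs.
- The Grade 3 bullet is permissive, and which Grade 3 rule to keep is a clinical choice.

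**Conclusion.** The inconsistency is real and sits in current text. For drug-related Grade 4 toxicity other than seizure or neurotoxicity, recovered within 7 days with doses left, the plan prescribes both permanent discontinuation and resumption at 240 mg a day (180 mg under the recurrence row). For the bounded set of first Grade 3 events it prescribes both 180 and 240 mg.

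The need to correct it rests on the Grade 4 case alone, and on the consequence of a wrong re-challenge rather than on how often it would occur. Few men, possibly none, would be affected. The case counts and cumulative-dose figures depend on assumed rates and timings; the daily-dose differences follow from the rules themselves, with 180 mg taken as the next lower level. No effect on the primary endpoint, the analysed set or the sample-size calculation is shown, and toxicity is graded and analysed the same way under either rule.

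**What to change.** Let the bullets govern and make Table 1 match them.

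1. Replace the row for Grade 3 or higher with two rows:
   - **Treatment-related Grade 3, first occurrence:** hold until Grade 1 or baseline. If recovered within 7 days, resume at 180 mg, or at the previous dose if controlled within 2 days. No hold for clinically insignificant laboratory abnormalities or hypertension, as judged by the treating physician.
   - **Any drug-related Grade 4:** discontinue permanently.
2. Restrict the recurrence row to Grade 3 and fit it to the limit of one reduction. A man still on 240 mg resumes at 180 mg. For a man already on 180 mg, state the action: discontinue, unless the clinical team specifies otherwise.
3. Add drug-related Grade 4 toxicity to the list in Section 9.16.

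If the clinical team prefers to resume at full dose after a first Grade 3 event, it should change the Grade 3 bullet instead and keep Grade 4 discontinuation in both places. Sections 5.1 and 14.1 need no change.

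The cost is one protocol amendment: two table rows reworded, one row added and one line added in Section 9.16. It needs no extra patients, visits or procedures.

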## 8 Pharmaceutical Information

[figure not shown]
### 8.1 Apalutamide

#### Molecular Formula and Chemical Class

Apalutamide drug substance is a white to off-white crystalline solid.

Chemical Name: (4-[7-(6-Cyano-5-trifluoromethylpyridin-3-yl)-8-oxo-6-thioxo-5,7-diazaspiro[3.4]oct-5-yl]-2-fluoro-N-methylbenzamide)

Chemical structure:

Molecular Formula: C21H15F4N5O2S

Molecular Weight: 477.44

